10.2. Withdrawal of Subjects From Study

Subjects must be withdrawn from the study for any one of the following reasons:

- The subject withdraws consent.
- The subject enrolls into another interventional clinical study in which an investigational treatment or approved therapy for investigational use is administered.
- The subject is unwilling or unable to comply with the protocol.

Subjects who are prematurely **withdrawn from the study** during the Double-blind Treatment Period should complete all study assessments for the ET Visit as soon as possible, but within 4 weeks. Withdrawn subjects should be encouraged to complete the study assessments for the Safety FU Visits at 4, 8, and 12 weeks after the ET Visit. However, if the subject is unwilling or unable to attend the study FU Visits, or at minimum the ET Visit, and decides to withdraw consent, the reason for withdrawal will be documented and no further assessments will be obtained.

The reason for the subject's withdrawal from the study must be recorded in the subject's eCRF. The level of consent withdrawal (e.g., whether samples collected but not yet analyzed can still be used/analyzed, and so on) should also be recorded in the eCRF.

CONFIDENTIAL

The information contained herein may not be used, disclosed, or published without the written consent of Biogen MA Inc.

11. STUDY TREATMENT USE

11.1. Study Treatment Regimen

11.1.1. Part A

Subjects will be randomized in a 1:1 ratio to 1 of the following 2 treatment groups:

- BIIB059 450 mg
- Placebo

Dose regimen: every 4 weeks (Q4W) SC, with an additional dose at Week 2, for a total of 7 doses.

11.1.2. Part B

Subjects will be randomized in a 1:1:1:1 ratio to 1 of the following 4 treatment groups:

- BIIB059 50 mg
- BIIB059 150 mg
- BIIB059 450 mg
- Placebo

Dose regimen: every 4 weeks SC (Q4W), with an additional dose at Week 2, for a total of 5 doses.

11.1.3. BIIB059

Biogen will provide BIIB059 to sites.

11.1.4. Placebo

Placebo (0.9% sodium chloride) will be commercially available saline supplied by the study site or Sponsor based on local regulations.

11.2. Study Treatment Precautions

Following administration of study treatment, subjects should remain at the study center for 1 hour to monitor for the development of potential allergic or anaphylactic reactions.

Epinephrine for SC injection, diphenhydramine (or equivalent) for IV injection, and any other medications and resuscitation equipment for the emergency management of anaphylactic reactions must be available in the room where the infusion is being performed.

BIIB059 or placebo should be administered within the stated window of the scheduled visit (± 2 or 3 days; see [Table 1](#) and [Table 2](#)). If a subject misses a planned dose (i.e., outside of the 2- or 3-day window), the missed dose should be administered as soon as possible, and no later than 5 days after the last day of the planned window. If the Week 2 dose (the second dose to be

CONFIDENTIAL

The information contained herein may not be used, disclosed, or published without the written consent of Biogen MA Inc.

administered in the study) can't be given within the planned window, the missed dose should be skipped and the subject should receive the next scheduled dose as per protocol.

11.3. Study Treatment Compliance

Compliance with treatment dosing is to be monitored and recorded by site staff.

11.4. Concomitant Therapy and Procedures

11.4.1. Concomitant Therapy

A concomitant therapy is any drug or substance administered between Screening and the final study visit.

11.4.1.1. Allowed Concomitant Therapy

All permitted therapies, unless indicated otherwise, should be taken at a stable dose starting from the Screening Visit until the end of the Treatment Period. A stable dose is defined as no increase or decrease during a specified time period. Dose decrease is allowed where specified by protocol.

Any medications, other than those excluded per Section 8.2, that are considered necessary for the subject's welfare and that do not interfere with the trial conduct or assessments, may be given at the Investigator's discretion and should be recorded in the eCRF dedicated page.

11.4.1.1.1. Background Therapies for Lupus

11.4.1.1.1.1. Systemic Lupus Erythematosus

Standard of care therapy that may be continued during the study for SLE includes 1 of the following single immunosuppressants or immunomodulators, delivered via IV, SC, or oral administration: azathioprine (up to 200 mg/day), 6-mercaptopurine (up to 100 mg/day), mycophenolate (either as MMF at up to 3 g/day or MPS up to 2160 mg/day), and methotrexate (up to 25 mg/week). Other permitted SoC therapies include antimalarial medications such as hydroxychloroquine (up to 400 mg/day), quinacrine (100 mg/day), chloroquine (up to 250 mg/day), and dapsone (up to 150 mg/day) as well as corticosteroids (see Section 11.4.1.1.2) and NSAIDs (see Section 11.4.1.1.3.1).

All background therapy for SLE given prior to Screening or randomization must have been kept stable or discontinued as specified in the inclusion/exclusion criteria for a subject to be eligible for the study. These medications must remain stable during Screening or randomization as well as the 24-week (Part A) or 16-week (Part B) Treatment Period, with the exception of the 2 corticosteroid rescue attempts allowed during corticosteroid tapering in Part A of the study (Section 11.4.1.1.2). No initiation of new immunosuppressant therapy or increase in dose of current immunosuppressant is allowed. Subjects who initiate SLE SoC therapy during the study will be considered treatment failures. They are encouraged to continue receiving study treatment and complete the study at the Investigator's discretion.

Standard of care medications that are part of the subject's previous SLE treatment will not be provided by Biogen.

CONFIDENTIAL

The information contained herein may not be used, disclosed, or published without the written consent of Biogen MA Inc.

11.4.1.1.2. Cutaneous Lupus Erythematosus

All background therapy for CLE given prior to Screening must have been kept stable or discontinued as specified in the inclusion/exclusion criteria (Section 8) for a subject to be eligible for the study. These medications must remain stable during the Screening Period as well as the Treatment Period.

11.4.1.1.2. Corticosteroid Usage During the Study

In Part A, corticosteroid use at doses above 20 mg/day of prednisone or prednisone equivalent is not allowed (with the exception of Rescue 1 during corticosteroid tapering; see [Table 7](#)). In Part B, corticosteroid use at doses above 15 mg/day of prednisone or prednisone equivalent is not allowed. Doses stated are for a total daily dose of prednisone or prednisolone; other corticosteroids may be used instead at the equivalent doses listed. See [Table 5](#) for prednisone equivalence values of commonly used corticosteroids.

Systemic (IM or IV) or intra-articular (Part A) administration of corticosteroids is not allowed for the duration of the study; a washout period of 12 weeks must be observed prior to randomization.

Nonsystemic corticosteroids (defined as otic, intranasal, inhaled, or ophthalmic) are permitted without restriction. See Section [11.4.1.1.2.1](#) for guidance on the use of topical steroids.

Table 5: Prednisone Equivalence Values for Common Alternatives

Medication	Equivalent (mg) to 1 mg of Prednisone
Betamethasone	0.15
Cortisone	5
Dexamethasone	0.15
Hydrocortisone	4
Prednisolone	1
Methylprednisolone	0.8
Triamcinolone	0.8

11.4.1.1.2.1. Topical and Intralesional Corticosteroids

Intralesional corticosteroids are not allowed during the screening and treatment periods. The use of low or lower mid-potency topical steroids is allowed during the study. [Table 6](#) provides guidance for topical corticosteroid use. Subjects are requested to avoid use of topical corticosteroids on the day of CLASI assessments throughout the study, and for 24 hours prior to the primary endpoint CLASI assessment at the Week 16 Visit.

High-potency steroids and/or topical agents (immunosuppressant) for skin lesions, including intralesional corticosteroids, are prohibited.

CONFIDENTIAL

The information contained herein may not be used, disclosed, or published without the written consent of
Biogen MA Inc.

Table 6: Topical Corticosteroids Allowed During the Study

Examples of Low-Potency or Lower Mid-Potency Topical Corticosteroids	
Low-Potency	Lower Mid-Potency
Hydrocortisone acetate 0.1 to 0.25%	Fluocinolone acetonide 0.025% cream
Desonide 0.05% cream	Triamcinolone acetonide 0.1%
Methylprednisolone 0.25%	Fluticasone propionate 0.05% cream
Fluocinolone acetonide 0.01%	Hydrocortisone butyrate 0.1% cream
	Betamethasone valerate 0.05%
	Clobetasone butyrate 0.05%.

For a list of commonly used topical corticosteroids that are not permitted during the study, see [Appendix B](#). The Investigator is invited to contact the Sponsor's Medical Monitor with questions about topical corticosteroid use during the study.

11.4.1.1.2.2. Part A Specific Instructions

Intra-articular Corticosteroids

Intra-articular administration of corticosteroids is not allowed for the duration of the study; a washout period of 12 weeks must be observed prior to randomization.

Oral Corticosteroids

Eligible subjects will have active SLE with joint and skin manifestations at Screening and randomization. Subjects may be treated with SLE background SoC therapies as per exclusion criterion #31 and, if taking corticosteroids, must have been on stable dosage for at least 4 weeks prior to randomization. Subjects who are not receiving corticosteroids at Screening or baseline are permitted to participate in the study.

Doses of corticosteroid must remain stable during Screening and during the first 4 weeks after the first dose of study treatment (i.e., until Day 28). The tapering schedule should begin 4 weeks (Week 5; Days 29 to 35) after the first dose of study treatment. The tapering regimen is intended to reduce the daily dose of prednisone (or equivalent) to 10 mg/day or lower by Week 12 (Day 85) of the study, as outlined in [Table 7](#).

If a subject deviates from the planned tapering schedule, they might be considered a treatment failure (see Section [16.1.2.1](#)). Subjects are allowed to continue to receive the investigational product and to complete the study at the discretion of the Investigator.

Subjects who achieve the Week 12 dose of 10 mg of prednisone (or equivalent) or lower may remain on this dose or continue to taper between Week 13 and Week 16 at the discretion of the Investigator. The dose of prednisone (or equivalent) will remain stable (at the Week 16 dose) between Week 17 and Week 24.

Screening:

Subjects who are receiving corticosteroids must receive a stable dose throughout the Screening period; no initiation, increase, or decrease of corticosteroid dose is permitted.

CONFIDENTIAL

The information contained herein may not be used, disclosed, or published without the written consent of Biogen MA Inc.

The maximum daily dose of corticosteroid allowed is 20 mg of prednisone (or equivalent).

Treatment period:

Oral corticosteroid dose tapering (as described in [Table 7](#)) is mandatory within the rules for dose changes outlined below.

Briefly, oral corticosteroids dosing guidelines are as follow:

- Stable corticosteroid dose from Day 1 to Week 4 (Day 1 to Day 28)
- Decrease in corticosteroid dose from baseline between Week 5 and Week 11 (Days 29 to 78)
- Stable corticosteroid dose at Week 12 (Days 79 to 85)
- Stable Week 12 corticosteroid dose, or decrease by 2.5 mg between Week 13 and Week 16 (Day 86 to 113)
- Stable corticosteroid dose (at Week 12 dose) between Week 17 and Week 24 (Days 114 to 169)

Between Day 1 to Week 4, the corticosteroid dose can be increased to a maximum of 10 mg/day above Day 1 dosage, but must return to Day 1 level within 7 days (Rescue 1). Between Week 5 and Week 7 (Rescue 2), OR between Week 9 and Week 11 (Rescue 3), the corticosteroid dose can be increased to the previous dosage level for up to 1 week before resuming the tapering schedule. Only two rescues out of the three described above are allowed, at the discretion of the Investigator.

Overall, TWO corticosteroid rescues are allowed:

- Rescue 1 and Rescue 2; OR
- Rescue 1 and Rescue 3; OR
- Rescue 2 and Rescue 3.

Any other increase in corticosteroid dose may be considered a treatment failure and/or a protocol deviation (depending on the timing or severity of the deviation) for the analysis (see [Section 16.1.2.1](#)). Subjects who cannot fulfill the corticosteroid tapering schedule should still complete the study and remain on the investigational product. Corticosteroid dose should be recorded in the subject diary ([Section 11.4.1.1.2.4](#)).

Day 1 to Week 4:

Stable dosage at Day 1 dose level, 1 oral corticosteroid rescue (Rescue 1) for SLE activity is allowed up to a dose no higher than 10 mg above the baseline level (maximum of 30 mg/day), but the dose must return to baseline (Day 1) level within 7 days. A dose increase is strongly recommended to be avoided within 1 week of a planned study visit.

Week 5 to Week 7:

Decrease as per the tapering schedule. One oral corticosteroid rescue (Rescue 2) for SLE activity is allowed up to a dose no higher than the previous dosage level, but the dose must be

CONFIDENTIAL

The information contained herein may not be used, disclosed, or published without the written consent of Biogen MA Inc.

returned to the last oral corticosteroid dosage prior to rescue level within 7 days. A dose increase is not permitted within 1 week of a planned study visit.

Week 8:

Decrease as per tapering schedule. No increases are allowed.

Week 9 to Week 11:

Decrease as per tapering schedule. One oral corticosteroid rescue (Rescue 3) for SLE activity is allowed up to a dose no higher than the previous dosage level, but the dose must be returned to last oral corticosteroid dosage prior to rescue level within 7 days. A dose increase is not permitted within 1 week of a planned study visit.

Week 12:

No increase or decrease allowed.

Week 13 to Week 16:

Stable dosage or decrease as per the tapering schedule (no increase is allowed). The corticosteroid dose must always be \leq Week 12 dose.

Week 17 to Week 24:

Stable dosage at Week 16 dosage, no increases or decreases are allowed.

CONFIDENTIAL

The information contained herein may not be used, disclosed, or published without the written consent of
Biogen MA Inc.

Table 7: Oral Corticosteroid Tapering Schedule

Allowable OCS Rescue Dosing ¹	Timing by Weeks (Days)	OCS Starting Dose Prior to Tapering (mg/day)							
		20 mg	17.5 mg	15 mg	12.5 mg	10 mg	7.5 mg	5 mg	2.5 to <5 mg
Rescue 1	Week 1-4 ² (Day 1 to 28)	Stable 1 OCS rescue for SLE activity allowed up to maximum 10 mg/day above Day 1 dosage, but must return to Day 1 level within 7 days							
Rescue 2	Week 5 ³ (Day 29 to 35)	17.5	15	12.5	10	7.5	5	5 or 2.5	2.5 to <5
	Week 6 ³ (Day 36 to 43)	17.5	15	12.5	10	7.5	5	5 or 2.5	2.5 to <5
	Week 7 ³ (Day 44 to 50)	15	12.5	12.5	10	7.5	5	5 or 2.5	2.5
	Week 8 (Days 51 to 57)	15	12.5	10	7.5	7.5	5	5 or 2.5	2.5
Rescue 3	Week 9 ³ (Days 58 to 64)	12.5	10	10	7.5	5	2.5	2.5	0 to 2.5
	Week 10 ³ (Days 65 to 71)	12.5	10	10	7.5	5	2.5	2.5	0 to 2.5
	Week 11 ³ (Days 72 to 78)	10	7.5	7.5	5	2.5 to <5	2.5	2.5	0 to 2.5
	Week 12 (Days 79 to 85)	10	7.5	7.5	5	2.5 to <5	2.5	2.5	0 to 2.5
	Week 13-16 (Days 86 to 113)	Stable at Week 12 dose or decrease							
	Week 17-24 (Days 114 to 169)	Stable at Week 16 dose							

Abbreviations: OCS = oral corticosteroids; SLE = systemic lupus erythematosus.

¹ Two rescues are allowed out of the three described.

CONFIDENTIAL

The information contained herein may not be used, disclosed, or published without the written consent of Biogen MA Inc.

² Between Weeks 1 and 4 (Rescue 1). Once a dose is reduced it must not be re-increased, with the exception of the 1 time rescue.

³ Between Weeks 5 and 7 (Rescue 2) and between Weeks 9 and 11 (Rescue 3), the dose can be increased to the previous dose level for up to 1 week before restarting the tapering schedule.

11.4.1.1.2.3. Part B Specific Instructions

Oral Corticosteroid

No corticosteroid tapering schedule is planned for subjects in Part B. The dose of corticosteroids given at Screening should not exceed 15 mg/day and should remain stable (no increase throughout the Screening, Treatment, and Follow-up Periods).

An increase of corticosteroid dose will be considered a treatment failure (see Section [16.1.2.1](#)). Subjects are allowed to remain in study and receive the investigational product.

11.4.1.1.2.4. Subject Diaries

Subjects will be issued a paper diary to record daily corticosteroid use (topical and oral) between study visits. Subjects will be instructed to bring the diary to the clinic at each visit, where it will be collected and reviewed by site personnel.

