Urinalysis (including microscopic examination)	X	X		X	X	X	X	X	X		X
Urine Protein-Creatinine Ratio (spot urine)	X	X		X	X	X	X	X	X		X
CD19+ B Cell Counts ¹⁶	X										
Pharmacokinetics											
Serum BIIB059 ¹⁷			X	X		X		X	X	X	X

CONFIDENTIAL

The information contained herein may not be used, disclosed, or published without the written consent of Biogen MA Inc.

CONFIDENTIAL

The information contained herein may not be used, disclosed, or published without the written consent of Biogen MA Inc.

	Screening Period	Treatment Period							Follow-up Period ¹			
		0	1	2	4	8	12	16/ ET	FU4	FU8	FU12	
Study Week	Within 4 Weeks Prior to Randomization	1 ³	8 (±2D)	15 ³ (±2D)	29 ³ (±3D)	57 ³ (±3D)	85 ³ (±3D)	113 (±3D)	141 (±5D)	169 (±5D)	197 (±5D)	
Tests and Assessments ^{2,3}												
Concomitant Medication/Procedures	Monitor and record from signing of informed consent through the end of the study											
Serious Adverse Events	Monitor and record from signing of informed consent through the end of the study											
Adverse Events			Monitor and record from time of first dose through the end of the study									

Abbreviations: ACR=American College of Rheumatology; C = complement; CLASI = Cutaneous Lupus Disease Area and Severity Index; CLE = cutaneous lupus erythematosus; CRP = C-reactive protein; D = day; DNA = deoxyribonucleic acid; dsDNA = double-stranded DNA; ECG = electrocardiogram; ESR = erythrocyte sedimentation rate; ET = early termination; FU = follow-up; HIV = human immunodeficiency virus; Ig = immunoglobulin; [REDACTED]; RNA = ribonucleic acid; [REDACTED]; SLE = systemic lupus erythematosus; SLEDAI-2K = Systemic Lupus Erythematosus Disease Activity Index; TB = tuberculosis; VAS = visual analog scale.

¹ Follow-up visits will be conducted 4, 8, and 12 weeks after the last Treatment Period Visit (Week 16 or ET).

² Assessments (e.g., CPK, ECG, etc.) may be performed as required to confirm SLEDAI-2K findings.

³ On each dosing day (Day 1, Day 15, Day 29, Day 57, and Day 85) all assessments should be performed prior to dosing.

⁴ To be performed locally.

⁵ Where mandated by local regulation, a chest x-ray will be obtained locally during the screening period, unless a previous chest x-ray or the documented results from a chest x-ray obtained within 12 weeks prior to screening are available. The chest x-ray or x-ray results will be reviewed by the Investigator (or designee) in order to exclude patients with active TB infection from entering the study.

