⁶ Testing to be performed locally. Indeterminate Quantiferon or T-SPOT tests may be repeated once, and will be considered positive if retest results are positive or indeterminate. Subjects with documented BCG vaccination must perform a tuberculosis test at Screening and will be excluded if they exhibit skin induration ≥5 mm or a positive Quantiferon or positive or borderline T-SPOT (Elispot) test.

⁷ To be performed locally.

⁸ Height should be measured only once; i.e., at the Day 1/baseline Visit.

⁹ Vital signs include seated arterial blood pressure, heart rate, and oral body temperature.

¹⁰ CLASI will be assessed by the Investigator or a trained designee at all assessments (Section 19.2.2). CLASI scores at Screening will be verified by an Independent CLASI Adjudicator to confirm eligibility.

[REDACTED]

[REDACTED]

[REDACTED]

¹⁴ Following administration of study treatment, subjects should remain at the study center for 1 hour to be observed for the development of potential allergic or anaphylactic reactions.

CONFIDENTIAL

The information contained herein may not be used, disclosed, or published without the written consent of Biogen MA Inc.

¹⁵ Subject paper diaries for recording corticosteroid use will be distributed on Day 1, reviewed with site staff at each study visit, and collected by the study site at the final study visit.

¹⁶ Only for subjects with prior B cell directed therapies within 52 weeks of Screening; this test should be performed at a central laboratory.

¹⁷ Pharmacokinetic evaluations will be conducted as follows: Day 1 (pre-dose -1 h and post-dose 4 h \pm 1 h), Day 8 (any time during the visit), Day 29 (predose -1 h and postdose 4 h \pm 1 h), Day 85 (predose -1 h and postdose 4 h \pm 1 h), and Day 113 (any time during the visit). During the Follow-up Period, 1 sample will be collected on Days 141, 169, and 197 (any time during the visit) [Table 3].

A large rectangular area of the page is redacted with black ink, obscuring several lines of text. To the left of this redacted area, there are four small, vertical black squares arranged in a column.

CONFIDENTIAL

The information contained herein may not be used, disclosed, or published without the written consent of Biogen MA Inc.

Table 3: Pharmacokinetic Assessments

Study Week	0	1	2	4	8	12	16	20	24	Follow-Up Period

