8.1.2. Inclusion Criteria (Part A Specific)

1. Diagnosis of SLE fulfilling at least 4 out of 11 of the 1997 revised ACR classification criteria for SLE ([Appendix C](#)), with a diagnosis made ≥ 24 weeks prior to signing the informed consent form (ICF).
2. Positive antinuclear antibody test at Screening (central laboratory titer $\geq 1:80$) and/or elevated anti-double-stranded DNA (≥ 30 IU/mL).
3. At least one sign of active skin disease, including acute, subacute, and/or chronic cutaneous lupus (e.g., discoid lupus erythematosus), with skin activity defined by SLEDAI-2K.
4. Must have at least 4 tender joints based on assessment of 28 joints as described in Section [4.3.3](#).
5. Must have at least 4 swollen joints based on assessment of 28 joints as described in Section [4.3.3](#), with at least 4 occurring in the PIP, MCP, or wrist joints. Note: A joint that is both tender and swollen will be included in both categories (counts as 1 tender and 1 swollen).
6. To allow for accurate assessment of joint tenderness and swelling, subjects who may be taking NSAIDs or other analgesics, including narcotics or medical marijuana, must agree not to take a dose of these medications within 24 hours prior to the joint assessment visits.

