8.1.3. Inclusion Criteria (Part B Specific)

1. Must have diagnosis of CLE that has been histologically confirmed (in the past or at Screening), with or without systemic LE manifestations. The histological diagnosis confirmation should be documented at Screening. For subjects without historical biopsy

CONFIDENTIAL

The information contained herein may not be used, disclosed, or published without the written consent of Biogen MA Inc.

data, a skin biopsy must be performed at Screening to confirm CLE diagnosis prior to randomization. All subjects must also have active skin manifestations that fulfill the following:

- Subacute CLE with a CLASI-A erythema score of ≥ 2
and/or
 - Chronic CLE, including DLE, with at least 1 active DLE lesion with a minimum CLASI-A erythema score ≥ 2 and in addition, CLASI-D scarring score ≥ 1
2. CLASI-A ≥ 8 at Screening and randomization.
 3. Must have active CLE despite an adequate trial of conventional therapies (defined as either topical corticosteroids or an antimalarial agent used for at least 12 weeks prior to Screening) OR previously documented failure to respond to these agents when used for at least 12 weeks OR the requirement to discontinue these agents due to side effects or poor tolerability.

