11.4.1.1.3. Pain Medication

11.4.1.1.3.1. Nonsteroidal Anti-inflammatory Treatments

Subjects taking stable doses of NSAIDs (e.g., ibuprofen, naproxen, aspirin) for SLE symptoms at Screening should continue to do so throughout the trial; however, subjects should refrain from using NSAIDs within 24 hours before each study visit. Subjects taking stable doses of NSAIDs for reasons other than SLE are encouraged to titrate down as tolerated.

Low-dose aspirin (<350 mg/day) at stable doses for cardiovascular prophylaxis is permitted during the study.

11.4.1.1.3.2. Acetaminophen

Acetaminophen (paracetamol) may be initiated for pain control of SLE symptoms during the study. The medication should be titrated down as tolerated. The maximum dose of acetaminophen or pain medications that contain acetaminophen is 3 g/day.

11.4.1.1.3.3. Other Pain Medications

Other pain medications, including opiates, other narcotics, and medical marijuana, may be used to treat symptoms of arthritis and other extra-articular conditions in SLE as needed; however, these medications may not be used within 24 hours of a study visit if they are used as needed. If opiates are chronically taken prior to Screening, a stable dose should be maintained from Screening until the end of the Treatment Period.

CONFIDENTIAL

The information contained herein may not be used, disclosed, or published without the written consent of Biogen MA Inc.

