16. STATISTICAL METHODS AND DETERMINATION OF SAMPLE SIZE

The objectives of the study and the endpoints to be analyzed are listed in [Table 4](#).

This is a 2-part study consisting of Part A and Part B.

For Part A, subjects will be randomized in a 1:1 ratio (50 subjects each to 450 mg and placebo), and the randomization will be stratified by prior oral corticosteroid usage (≤ 10 mg/day vs. > 10 mg/day) and by geographic region (United States vs. Asia vs. Latin America and Europe). This randomization scheme will apply to the approximately 100 subjects randomized under protocol version 2 or subsequent versions.

For Part B, subjects will be randomized in a 1:1:1:1 ratio (25 subjects each to 50 mg, 150 mg, and 450 mg and placebo), and the randomization will be stratified by CLASI-A score (≤ 10 vs. > 10) and DLE (presence, absence). This randomization scheme will apply to the approximately 100 subjects randomized under protocol version 2 or subsequent versions.

For Part A and Part B, baseline is defined as the last nonmissing measurement prior to randomization to study treatment (Screening or Day 1), change from baseline is defined as post-baseline value minus baseline value, and percent change is defined as $100 \times (\text{change}/\text{baseline})$.

For each part, all primary, secondary and exploratory endpoints will be summarized by treatment group and, where applicable, by treatment group and visit, unless otherwise specified in the SAP.

Additional information is provided in the subsections below, analysis details will be provided in the SAP.

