4.3. Visit/Analysis Week Definitions

The definition of visits below applies to both parts A and B.

Baseline

Baseline will refer to the last non-missing value prior to the first randomized dose.

Treatment Day [TD] (Days relative to the first randomized dose)

To facilitate the analysis of the data in the treatment period (TP), TD will be calculated for each day in the study as the number of days between the date of the first randomized dose and the specific day of interest. For a day that is on or after the day of the first randomized dose, the TD is a positive value and will be calculated as (date of study day – date of the first randomized dose +1). For a day that is prior to the date of the first randomized dose, the TD is a negative value and will be calculated as (date of study day – date of the first randomized dose). The study starts at TD1.

Analysis Week

Observations that are collected after the first randomized dose as scheduled visit will be used to the corresponding analysis week. Baseline corresponds to “Week 0” in the protocol or the latest non-missing value prior to first study drug administration if Week 0 assessment is missing.

Data from Early Termination or Unscheduled Visits

In general, when data are summarized by visit/analysis week, the Early Termination Visit or Unscheduled Visit will be assigned to an appropriate scheduled visit/analysis week (PV2 or later) by using a window scheme as follows.

CONFIDENTIAL

The information contained herein may not be used, disclosed, or published without the written consent of Biogen MA Inc.

The lower bound and the upper bound for the visit windows are defined as the midpoints of the scheduled visits (PV2 or later). If the date and time from early termination visit falls in between the lower bound and the upper bound for a scheduled visit, then it will be assigned to that visit. If there are 2 or more assessments available in the same analysis window for a subject, the assessment that is closest to the target visit day will be used for analysis. If there are 2 or more assessments in the same analysis window with the same distance from the target visit day, the earlier assessment will be used.

The windowing scheme for the primary endpoint in Part A and Part B is shown in [Table 2](#) and [Table 3](#) below.

CONFIDENTIAL

The information contained herein may not be used, disclosed, or published without the written consent of Biogen MA Inc.

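### Part B asks for 24 topical-steroid-free hours before the Week 16 CLASI but only same-day avoidance before the Day 1 CLASI, which will nearly always be the baseline of the primary percent change

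*Protocol*

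**What the plan says.** Protocol 11.4.1.1.2.1 permits low and lower mid-potency topical steroids (Table 6) during the study. It words its request to subjects as "avoid use of topical corticosteroids on the day of CLASI assessments throughout the study, and for 24 hours prior to the primary endpoint CLASI assessment", and ties that last assessment to the Week 16 Visit. The 24-hour window is not extended to any other visit.

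The Part B primary endpoint is the percent change in CLASI-A from baseline to Week 16. SAP 4.3 states: "Baseline will refer to the last non-missing value prior to the first randomized dose". Protocol section 16 likewise takes the last available value before randomization, from Screening or Day 1. Protocol 8.1.3 requires CLASI-A of at least 8 "at Screening and randomization", and Table 2 footnote 3 puts Day 1 assessments before dosing. A valid Day 1 score should therefore exist for almost every randomized subject, and it will be the baseline.

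Part A treats its primary endpoint differently. Under Protocol 8.1.2, subjects on NSAIDs or other analgesics "must agree not to take a dose of these medications within 24 hours prior to the joint assessment visits". Section 11.4.1.1.3.1 adds that "subjects should refrain from using NSAIDs within 24 hours before each study visit". Both rules cover the baseline visit as well as Week 24.

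**The concern.** A percent change has two ends, and here they are measured under different conditions. With a morning visit, applying a Table 6 product the evening before is compatible with the request on Day 1 but not at Week 16. Such use is realistic. Topical corticosteroids are one of the qualifying prior therapies in Protocol 8.1.3, and permitted therapies are meant to stay at a stable dose from Screening (11.4.1.1).

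The 24-hour rule at Week 16 makes sense only if previous-day use could affect the score. If it could, the same holds for the denominator. A suppressed baseline would make every arm look less improved at Week 16 than it is. It would lower CLASI-50 rates and, because the denominator is too small, stretch the difference between arms in percentage points. The fitted dose-response model is to be used to estimate target doses (SAP 6.2.1), so the size of the effect matters as well as the test.

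**Working it through.** **1. Do other rules equalise the time since last application?**
- Exclusion criterion 24 (Protocol 8.2.1) gives a 7-day washout, but for high-potency topicals and topical immunosuppressants only.
- The stable-dose rules (11.4.1.1, and the CLE background therapy section) fix the regimen, not the hours since the last application.
- The photography instruction (4.3.4) is also same-day only.
- SAP 5.8 exempts Table 6 products from the treatment-failure rule.
- Concomitant medication is covered by "Monitor and record from signing of informed consent through the end of the study", so a topical in use at baseline is recorded. The protocol does not ask for the time of the last application before the Day 1 CLASI.
- The diary cannot supply that time: "Subject paper diaries for recording corticosteroid use will be distributed on Day 1, reviewed with site staff at each study visit".

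None of these closes the gap.

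**2. The plan's own figure.** Protocol 16.8 gives about 90% power for Part B (SD 30, maximal difference 27.5, 25 per arm, 20% dropout, two-sided 10%). Simulating the MCP-Mod test with the five SAP candidate models and 20 per arm gives 89.1% to 94.1% across the shapes. The pairwise check of one dose against placebo gives 89.5%. The stated power reproduces, and the point does not depend on it.

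**3. Size of the distortion at Week 16.** From the documents: difference 27.5, SD 30. Assumed: baseline reads low by a share s in a fraction p of subjects, there is no suppression at Week 16, true mean improvement is 20% on placebo (hence 47.5% on drug), and improvements are normally distributed.
- Measured improvement in an affected subject with true improvement m: 100 − (100 − m)/(1 − s). The SD becomes 30/(1 − s).
- Arm difference: 27.5 × [1 + p·s/(1 − s)].
- Example with p = 1, s = 0.10: placebo 100 − 80/0.9 = 11.1; drug 100 − 52.5/0.9 = 41.7; difference 27.5 × 1.111 = 30.56; SD 30/0.9 = 33.33; standardised effect 30.56/33.33 = 0.917.

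| p, s | Mean improvement, placebo / drug (%) | Difference | Pooled SD | Standardised effect | CLASI-50, placebo / drug (%) |
|---|---|---|---|---|---|
| none | 20.0 / 47.5 | 27.50 | 30.00 | 0.917 | 15.9 / 46.7 |
| 0.25, 0.05 | 18.9 / 46.8 | 27.86 | 30.44 | 0.915 | 15.4 / 45.9 |
| 0.50, 0.10 | 15.6 / 44.6 | 29.03 | 31.93 | 0.909 | 14.0 / 43.4 |
| 1.00, 0.10 | 11.1 / 41.7 | 30.56 | 33.33 | 0.917 | 12.2 / 40.1 |

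With the placebo mean varied from 0% to 30%, the lowest standardised effect is 0.905.

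**4. One subject, one point.** If a true baseline B reads B − 1, percent change shifts by 100 × (1 − m)/(B − 1), with m the true improvement as a proportion. For B = 9 the shift is 6.3 points at m = 0.5 and 10.0 points at m = 0.2. For B = 16 it is 3.3 and 5.3 points.

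**5. What happens if only Day 1 is changed.** Week 12 and the earlier visits would keep the same-day rule, so suppression would sit in the numerator only. The difference becomes 27.5 × (1 − p·s), borrowing the Week 16 value for Week 12. This gives 27.16 at p = 0.25, s = 0.05, and 24.75 at p = 1, s = 0.10. In the latter case true improvements of 20% and 47.5% read 100 − 80 × 0.9 = 28% and 100 − 52.5 × 0.9 = 52.75%. Under the present text, proportional suppression at Day 1 and Week 12 cancels.

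**The case against.** The strongest reply is that no harm is documented. Nothing in the protocol or SAP says that a weak topical used the evening before changes a CLASI-A score. The suppression, the share of subjects affected and the placebo mean are all assumed, and the top of the range needs every subject affected at 10%. Part B also recruits subjects with active CLE despite, or intolerant of, topical steroids or an antimalarial, which makes large overnight effects less plausible without ruling them out. All of this stands, and it limits the severity.

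A reader might go further and infer that the unequal windows bias the randomised comparison or could create a treatment effect. The documents do not support that. The request is the same in all arms and the baseline precedes randomization, so no difference arises under the null. The MMRM also adjusts for baseline and baseline-by-visit (SAP 6.1.2), whereas the figures above are unadjusted. A reader might also infer that topical use at baseline goes unrecorded. It does not; only its timing is missing.

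The Part A comparison is imperfect. It concerns analgesics and joints, and 11.4.1.1.3.3 limits the 24-hour rule for other pain medications to as-needed use, with chronic opiates continued at a stable dose. It shows that a window covering both ends was workable in this trial, no more.

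Finally, the Study Reference Guide and the CLASI adjudication charter are not available and could hold further Day 1 instructions.

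**Conclusion.** The mismatch is real on the text: 24 hours at Week 16, same-day only at the usual baseline, and no other rule that equalises the two. Its effect depends on whether previous-day use of a Table 6 product moves CLASI-A. If it does not, every shift is zero. Over the assumed range, drug-arm CLASI-50 falls from 46.7% to between 45.9% and 40.1%, and the arm difference rises by 0.4 to 3.1 points. The dose-response test is essentially untouched. The reported size of the effects is what is exposed, and the gap could not readily be checked afterwards. This is a cheap improvement of low severity.

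**What to change.** In Protocol 11.4.1.1.2.1, request avoidance of topical corticosteroids for 24 hours before every Part B CLASI assessment from Day 1 through Week 16. Covering all these visits keeps the Week 12 secondary endpoints and the other MMRM visits matched to baseline. Week 12 also matters for the futility look, which is triggered by Week 12 completion. Apply the request at Screening only where that CLASI is done at least a day after consent, since consent must come before any screening test (9.1). Optionally, record at Day 1 a yes/no on topical steroid use in the previous 24 hours.

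The cost is one sentence, updated visit-reminder text and, if adopted, one case report form item. Subjects accept a slightly longer restriction on weak topicals before each CLASI visit, as they already do at Week 16. Sample size, significance level and analysis model do not change.
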